5.5 Baseline

If subjects had not received other anti-cancer therapies and not reached progressive disease when they enrolled in study 010, baseline disease assessments from the initial study will be used for baseline values for determining response and progression unless no prior assessments were collected (eg, PX-171-008). For those subjects who didn't have baseline collected in prior study, tumor assessments will be conducted at the time of screening for the current study using the appropriate method. And for those who received other anti-cancer therapies and/or progressive disease when they enrolled in study 010, baseline values from current study will be used.

During the study, the addition of certain approved agents with known antitumor activity or increase of carfilzomib dose and/or frequency is permitted if there is concern for disease progression and per Investigator discretion in consultation with the Onyx Medical Monitor. If it happens, measurements at the time of addition of new agents will be used as new baseline.

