7.7.1 Overall Survival (OS)

Duration of OS is defined as the days from the start of treatment (initial study) to death due to any cause. For subjects who are alive at the time of the data cut-off, duration of OS will be censored as of the date the subject was last known to be alive.

Since the subjects will be followed up till 30 days after administration of last dose of study drug only per protocol, OS will be calculated and presented in a listing, no Kaplan-Meier estimates will be provided. Number and percentage of subjects who died within 30 days after administration of last dose of study drug will be calculated and death reason will be summarized.

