7.7.2 Progression Free Survival (PFS)

PFS is defined as number of days between start of treatment and first evidence of documented disease progression or death (due to any cause), whichever occurs first. Disease progression will be determined by the local investigator for regimens with the same baseline using the International Uniform Response Criteria ([Durie et al. 2006, with corrections](#)) (IMWG-URC) for multiple myeloma subjects and RECIST criteria ([Therasse et al. 2000](#)) for solid tumor subjects. PFS will be re-calculated whenever the baseline is reset due to addition of new anti-cancer therapy or increase of carfilzomib dose/frequency:

- 1) For regimens that continue from initial study without baseline being reset, if subjects didn't progress before PX-171-010, then PFS for the period from initial study to PX-171-010 study will be calculated as Disease Progression /Death Date – Date of first dose in initial study + 1 day, and PFS for the period of PX-171-010 study only will be calculated as Disease Progression /Death Date – Date of first dose in PX-171-010 + 1 day.
- 2) For regimens that start in PX-171-010 study with baseline being reset from initial study or previous regimens, PFS will be calculated as Disease Progression /Death Date –

Date of first dose in the first regimen among the regimens with common baseline + 1 day.

PFS will be right-censored for subjects who met one of the following conditions: 1) no baseline disease assessments or any post-baseline assessments, 2) alive and does not have documentation of disease progression before a data analysis cutoff date. The PFS censoring rules are described in Table 1.

Table 1. Censoring Rules for PFS Analysis

Situation	Date of Progression or Censoring	Outcome
No baseline disease assessments or any post-baseline assessments	Date of first dose	Censored
Alive and without documentation of disease progression	Date of last disease assessment	Censored
Death or disease progression between planned disease assessments	Date of death or first disease assessment showing disease progression, whichever occurs first	Progressed
Death or PD immediately after more than 1 consecutively missed disease assessment visit*	Date of last disease assessment before the first missed visit	Censored
Death before first disease assessment	Date of death	Progressed

* If death or PD is more than 168 days after previous disease assessment, or the first dosing date if there is no previous disease assessment.

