The number and percentage of subjects with events, the number and percentage of subjects censored will be calculated for each disease cohort (MM, solid tumor) by regimen. The denominator for each regimen will be subjects who had the regimen.

Kaplan-Meier method will be used to estimate the distribution of PFS. The 25%, 50% and 75% KM quartiles will be provided along with a two-sided 95% confidence interval ([Klein and Moeschberger, 1997](#)).

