7.7.3 Time to Progression (TTP)

TTP is defined as number of days between start of treatment to the first documentation of disease progression. TTP will be re-calculated whenever the baseline is reset due to addition of new anti-cancer therapy or increase of carfilzomib dose/frequency:

- 1) For regimens that continue from initial study without baseline being reset, if subjects didn't progress before PX-171-010, then TTP for the period from initial study to PX-171-010 study will be calculated as Date of Disease Progression – Date of first dose in initial study + 1 day, and TTP for the period of PX-171-010 study only will be calculated as Date of Disease Progression – Date of first dose in PX-171-010 + 1 day.
- 2) For regimens that start in PX-171-010 study with baseline being reset from initial study or previous regimens, TTP will be calculated as Date of Disease Progression – Date of first dose in the first regimen among the regimens with common baseline + 1 day. The same censoring rules, except for death, as in analysis of PFS ([Section 7.7.2](#)) will be applied in calculation of TTP. Subjects who die before disease progression will be censored at death date.

The number and percentage of subjects with events, the number and percentage of subjects censored will be calculated. Kaplan-Meier method will be used to estimate the distribution of TTP for each disease cohort by regimens. The 25%, 50% and 75% KM quartiles will be provided along with a two-sided 95% confidence interval ([Klein and Moeschberger, 1997](#)).

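### For regimens that continue without a baseline reset, PFS and TTP counted from the first parent-study dose keep only subjects progression-free at rollover, yet ordinary Kaplan-Meier treats them as at risk from day 1 with no delayed entry and no conditional label

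*SAP*

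**What the plan says.** SAP 7.7.2 opens with a general definition: "PFS is defined as number of days between start of treatment and first evidence of documented disease progression or death". Rule 1 then covers regimens that continue from the parent study with the same baseline. It gives each eligible subject two durations:

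- **Duration (a)**, from first dose in the parent study: "if subjects didn't progress before PX-171-010, then PFS for the period from initial study to PX-171-010 study will be calculated as" event date minus that dose date, plus one day.
- **Duration (b)**, from first dose in the extension: "and PFS for the period of PX-171-010 study only will be calculated as Disease Progression /Death Date" minus first PX-171-010 dose date, plus one day.

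SAP 7.7.3 repeats the pair for TTP: "then TTP for the period from initial study to PX-171-010 study will be calculated as Date of Disease Progression" minus first parent-study dose date, plus one day.

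Subjects who had already progressed leave this group. Under SAP 5.5, for "those who received other anti-cancer therapies and/or progressive disease when they enrolled in study 010, baseline values from current study will be used". SAP 4.2 draws the full analysis set only from subjects enrolled in PX-171-010.

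On estimation the SAP says "Kaplan-Meier method will be used to estimate the distribution of PFS" and "Kaplan-Meier method will be used to estimate the distribution of TTP for each disease cohort by regimens", with quartiles and two-sided 95% intervals. It does not say which duration leads. Table 1 deals with right-censoring only. Neither document mentions delayed entry, left truncation or a landmark.

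**The concern.** To contribute to (a), a subject must have reached the extension without progressing. The time from first parent-study dose to first extension dose is therefore guaranteed event-free. Parent-study subjects who progressed or died in that interval are absent from both numerator and risk set. Ordinary Kaplan-Meier still counts every retained subject as at risk from day 1. This is immortal time written into a stated rule, not a detail left for later.

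At stake is how two of the three secondary endpoints are read. A median of (a) presented as PFS or TTP from start of carfilzomib would depend partly on how long the parent studies and the gap lasted, not only on how long the drug holds the disease.

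**Working it through.** The plan gives no expected PFS, event count or power, so there is no figure to reproduce. The check has four parts: direction, size, the limit on direction, and what the alternatives recover.

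**Inputs from the documents.** Parent-study treatment maxima range from 1 to 18 cycles (Protocol 1.4). First extension dose falls within 90 days of parent-study completion (Protocol 4.1). Cycles were 28 or 14 days (Protocol 1.2).

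**Assumptions.** True medians of 180, 270 and 365 d. Weibull survival S(x) = exp(−(x/λ)^k), with λ = median/(ln 2)^(1/k) and k = 2, 1 or 0.7 (rising, constant or falling hazard). Rollover times r = 28, 56, …, 504 d (18 equally likely values), unrelated to progression risk. No gap and no censoring in the base case.

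**Direction.** If rollover time R is independent of progression time, ordinary Kaplan-Meier on (a) estimates

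S_a(x) = E[S(max(x,R))] / E[S(R)].

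Since S(max(x,R)) = min(S(x),S(R)) ≥ S(x)·S(R), it follows that S_a(x) ≥ S(x) for every x. No quartile can then be too low. For (b), S_b(x) = E[S(x+R)] / E[S(R)].

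**One case by hand (k = 1, true median 180 d).** ΣS(r) = 7.522. At x = 393, the 14 rollover times up to 392 d each contribute 0.2202 (3.082 in total) and the four later ones contribute 0.680. The ratio is 3.762/7.522 = 0.50, so the median of (a) is 393 d, and 393/180 = 2.18.

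**Size, base case (medians in days, for true medians 180 / 270 / 365).**

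| Hazard | (a) | (a) ÷ truth | (b) |
|---|---|---|---|
| Rising, k = 2 | 239 / 352 / 455 | 1.33 / 1.30 / 1.25 | 98 / 153 / 219 |
| Constant, k = 1 | 393 / 509 / 611 | 2.18 / 1.89 / 1.67 | 180 / 270 / 365 |
| Falling, k = 0.7 | 543 / 673 / 802 | 3.0 / 2.5 / 2.2 | 303 / 427 / 551 |

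The lower quartile suffers most in relative terms. At k = 1 and true median 180 d, the quartiles of (a) are 238/393/587 d against a true 75/180/360 d.

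**Variants.** With 14-day cycles and no gap, the smallest ratio is 394/365 = 1.08 (k = 2). With 28-day cycles and a 90-day gap, the largest is 668/180 = 3.7 (k = 0.7). Every setting with spread rollover gives a ratio above 1. Simulated censoring, uniform over 0–720 d after rollover, does not remove the excess: at true median 180 d the medians of (a) are 243, 409 and 563 d.

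If everyone rolled over at a single time, the range would be wider. At true median 180 d, the median of (a) runs from 182 d (one 28-day cycle, k = 2; 1.01 times) to 888 d (18 cycles, k = 0.7; 4.9 times).

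**Limit on direction.** Suppose instead that rolling over depends on prognosis. Take a 50:50 mix of exponential medians 540 and 180 d, rollover at day 56, and enrolment of 30% of the eligible better-prognosis subjects and all of the eligible others. The retained weights are 0.5 × 0.3 × exp(−56 ln 2/540) = 0.140 and 0.5 × exp(−56 ln 2/180) = 0.403. The true quartiles are 116/298/669 d and those of (a) are 148/284/546 d. The lower quartile is still too high, but the median and upper quartile fall below the truth.

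**What the alternatives recover.** Delayed entry at first extension dose, in a large base-case sample with true median 180 d, gives 182, 208 and 254 d for k = 2, 1 and 0.7. It stays somewhat high because nothing is observed before day 28. With an assumed 50 subjects and k = 1, its 95% simulation range is 53–333 d, with on average 5.9 at risk on day 29. Duration (b) ranges over 119–258 d.

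**The case against.** The strongest reply is that (a) is biased only against a target the SAP does not clearly claim. The objective concerns subjects who completed a parent study, rule 1 states its own condition, and it names (a) as covering the period from the parent study to the extension. Nor is (a) plainly the main PFS. For OS the SAP spells out the origin, "Duration of OS is defined as the days from the start of treatment (initial study) to death due to any cause", but the opening PFS and TTP definitions lack that parenthesis. SAP 5.1 and 5.2 anchor timing at first dose in this study unless stated otherwise. Much of this stands: start of carfilzomib is a natural reading of (a), not the only one. As a summary of total progression-free time among subjects who rolled over, (a) is defensible and useful in a long-term study. But the Kaplan-Meier text carries neither that label nor an adjusted risk set, so the condition is lost where the result is reported.

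Two further replies also hold. Duration (b) is already prespecified for the same subjects, so this is not a plan without a usable clock. And neither (b) nor delayed entry is a clean substitute: (b) equals PFS from start of carfilzomib only under a constant hazard, and delayed entry is thin early.

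A reader might infer that every quartile of (a) must be too high. The documents do not support that. Enrolment also requires parent-study completion, consent and no intervening chemotherapy, and nothing shows that these are unrelated to prognosis. A reader might also infer an inflated error rate or a threat to the safety conclusions. Protocol 10.1 sets no hypothesis to test, and the primary endpoints are safety endpoints that this rule does not touch.

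**Conclusion.** The point holds for rule 1 of SAP 7.7.2 and 7.7.3 and should be corrected before Kaplan-Meier output is produced. It is certain from the text that no event in (a) can precede rollover, so the curve is flat up to the earliest rollover and inflated by subjects not yet rolled over. It is conditional that the quartiles are too high as PFS or TTP from start of carfilzomib: this requires rolling over and its timing to be unrelated to later progression risk. That direction is likely, but the median or upper quartile could go the other way under selective rollover.

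The size is not derivable from the documents. The 1.08 to 3.7 range rests on the assumed medians, Weibull shapes and evenly spread, unrelated rollover; it is not a bound. The consequence is a misleading descriptive estimate and nothing more. Rule 2 regimens are outside this point, and so is OS, which the SAP presents as a listing without Kaplan-Meier. The different time origin in Protocol 10.4.2 is a separate matter.

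**What to change.** In rule 1 of SAP 7.7.2 and 7.7.3:

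1. Name (b) as the lead Kaplan-Meier estimate, labelled *time from first PX-171-010 dose, conditional on being progression-free at rollover*.
2. Treat (a) in one of two ways. Either enter each subject in the risk set at first PX-171-010 dose, show numbers at risk, and state that the curve is conditional on rollover, imprecise early and dependent on rollover timing being unrelated to later risk. Or present (a) only as descriptive total progression-free time among rollover subjects, stated not to be PFS or TTP from start of carfilzomib.
3. State that neither (b) nor delayed entry fully recovers PFS or TTP from start of carfilzomib.

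Leave rule 2 and the OS listing unchanged.

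The cost is a few sentences in two sections and, if the delayed-entry curve is chosen, one entry-time variable. Both first-dose dates are already in the rule 1 formulas. The likely downside is that the reported medians look less favourable.

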7.4 Regimen Change

The number and percent of subjects who had regimen change during the study and reasons for regimen changes will be summarized as collected on regimen change case report form. In addition, type of regimen changes: carfilzomib dose level increased/decreased, dose frequency increased/decreased, or other anti-myeloma drugs added will be summarized .

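### SAP 7.7.2 and 7.7.3 report PFS and TTP by regimen but never start the clock at a reduced regimen's own first dose, so read literally a reduced regimen is credited with progression-free time from the regimen before it

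*SAP*

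**What the plan says.** **What counts as a regimen change.** SAP 7.4 says the "type of regimen changes: carfilzomib dose level increased/decreased, dose frequency increased/decreased, or other anti-myeloma drugs added will be summarized". Decreases are on that list, and Protocol 6.2.1 permits reductions of both dose level and dose frequency.

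**What resets the baseline.** SAP 7.7.2 states: "PFS will be re-calculated whenever the baseline is reset due to addition of new anti-cancer therapy or increase of carfilzomib dose/frequency". SAP 7.7.3 says the same for TTP, and SAP 5.5 names the same two triggers. A decrease is not among them.

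**Where the clock starts.** SAP 7.7.2 and 7.7.3 give two rules.
- Rule 1 covers regimens that carry on from the initial study without a reset. It gives two durations: one from the first dose in the initial study, and one in which "PFS for the period of PX-171-010 study only will be calculated as Disease Progression /Death Date – Date of first dose in PX-171-010 + 1 day".
- Rule 2 covers regimens that start in PX-171-010 after a reset. The origin is the "Date of first dose in the first regimen among the regimens with common baseline".

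**How results are reported.** PFS events and censorings "will be calculated for each disease cohort (MM, solid tumor) by regimen". The next sentence reads: "The denominator for each regimen will be subjects who had the regimen". For TTP, "Kaplan-Meier method will be used to estimate the distribution of TTP for each disease cohort by regimens". The PFS Kaplan-Meier sentence does not repeat the split by regimen.

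**The concern.** A subject can reach a reduced regimen without a new baseline only by being progression-free at the switch. If that regimen has its own row, and the row is timed from an earlier regimen's first dose, the time before the switch is immortal time: no one in the row could have progressed during it, yet all of it counts toward the row. The subject is also in the earlier regimen's row, because that denominator takes everyone who had the regimen. Nothing in the PFS censoring table or the TTP text closes the earlier regimen at the switch, applies delayed entry, or assigns an event to a single regimen.

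At stake is how the by-regimen tables are read. A reduced regimen could show longer times than the one it replaced with no true difference between them, and events summed over rows could exceed the number of progressions and deaths. This arises inside PX-171-010 alone, whatever is decided about counting time from the initial study.

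**Working it through.** The documents state no PFS or TTP figure to reproduce. The check applies the SAP's date rules to a reduced regimen B that follows regimen A on the same baseline.

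**1. A case squarely within rule 2.** A subject's dose is increased in PX-171-010, which resets the baseline and starts A. Frequency is cut 6 months after A's first dose, which starts B without a reset. Progression comes at month 14.
- Time on B: 14 − 6 = 8 months.
- Duration under rule 2, for A and B alike: 14 months.
- Denominators containing the subject: two.
- Rows in which the one progression can appear as an event: two.

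A reduction in PX-171-010 with no earlier reset fits neither rule exactly. Rule 1 is the nearer, and both of its origins also precede B's first dose.

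**2. Time credited to B before it starts.** Credit = (first dose of B) − (SAP time origin). Assume B starts after k = 3, 6 or 12 cycles of 28 days, counted from the reset (rule 2) or from entry to PX-171-010 (rule 1).
- Rule 2, or the PX-171-010-only version of rule 1: 28k = 84, 168 or 336 days.
- Rule 1 from the initial study: 28 × (initial cycles) + gap + 28k. Protocol 1.4 gives maximum treatment durations of 1 to 18 cycles in the earlier studies, and Protocol 4.1 allows up to 90 days before the first PX-171-010 dose.
  - Low end: 28 × 1 + 0 + 28 × 3 = 112 days.
  - High end: 28 × 18 + 90 + 28 × 12 = 504 + 90 + 336 = 930 days.

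The 28-day length for initial-study cycles is an assumption. Protocol 1.2 describes 14-day cycles in PX-171-001, for which the credit would be smaller.

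**3. Effect on a median.** Assume a constant progression hazard λ, the same on A and B, and that every subject still progression-free at time s switches to B. With m = ln 2 / λ, for t > s:

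P(T > t | T > s) = exp(−λ(t − s))

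Setting this to 1/2 gives t = s + m. With m = 12 months:

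| Switch at month s | Median for B on the SAP clock | From B's own first dose | Apparent gain |
|---|---|---|---|
| 3 | 3 + 12 = 15 | 12 | 3/12 = 25% |
| 6 | 6 + 12 = 18 | 12 | 6/12 = 50% |
| 12 | 12 + 12 = 24 | 12 | 12/12 = 100% |

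Row A holds everyone and is not censored at the switch, so its median is also 12 months.

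**4. Simulation check.** Two million exponential times were drawn per scenario. With a true median of 336 days and switches at day 84, 168 and 336, B's median on the SAP clock was 420, 504 and 672 days, against 336 from its own first dose each time. These equal s + m. True medians of 168 and 504 days followed the same formula to within simulation error.

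**The case against.** The strongest reply is that regimen is nowhere defined. SAP 7.4 summarizes changes recorded on a case report form; it does not say that each one makes a row in 7.7. The efficacy text is built around baseline groups: progression and best response are determined for regimens sharing a baseline, and PFS is recalculated only at a reset. A decrease would then trigger no new calculation, and each baseline group would yield one PFS time per subject. If that is the intention, the problem disappears.

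This reading is possible, but the reporting sentences work against it. The denominator is set by having had the regimen, not by belonging to a baseline group. Rule 2 speaks of a first regimen among several with one baseline, so a group can hold more than one. SAP 7.5 reports treatment duration and average and cumulative dose by regimen, which treats a regimen as a dosing segment. No sentence pools common-baseline regimens into one row.

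Other parts of the reply stand. The split by regimen is explicit for PFS counts and TTP Kaplan-Meier only. A reader might infer that the SAP prescribes biased by-regimen PFS curves, but the PFS Kaplan-Meier sentence does not say so. A reader might also infer a planned contrast of full against reduced carfilzomib. None is planned: Protocol 10.1 tests no hypothesis, and PFS and TTP are secondary endpoints. Finally, the documents give neither the number nor the timing of reductions, so the medians above show possible size, not expected size.

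**Conclusion.** The point holds on a literal reading. Every stated time origin precedes a reduced regimen's first dose. TTP reported for that regimen therefore includes progression-free time from the earlier regimen, and PFS does too if its Kaplan-Meier estimate is also split by regimen. One progression, or for PFS one death, can be counted as an event under more than one regimen.

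The credited time equals the interval from the SAP origin to the switch. The apparent medians of 15, 18 and 24 months against 12 rest on a constant hazard, no regimen effect and a single switch time for everyone still progression-free. If switching is related to prognosis, for example because reductions follow toxicity, the apparent gain could differ.

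It would go too far to conclude that reduced regimens will look better in the final report. That depends on how regimen is interpreted and on switch patterns the documents do not give. With no hypothesis test, neither type I error nor power is affected. The change should still be made before analysis, because the SAP states a reporting rule that can mislead and contains nothing that prevents it.

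**What to change.** In SAP 7.7.2 and 7.7.3:
1. Define regimen, and make the reporting row the baseline period, meaning all consecutive regimens that share a baseline. Label each period by its starting regimen.
2. Give each subject one record, one origin and at most one event per period.
3. Replace the denominator rule with the number of subjects who entered the baseline period.
4. State that the PFS Kaplan-Meier estimate uses the same rows as the PFS counts and TTP.
5. Say which rule covers a reduction within PX-171-010 when there has been no reset.

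If a separate result for a reduced regimen is still wanted, start its clock at that regimen's first dose, or keep the common origin and use delayed entry at that date. Censor the earlier regimen at the switch and assign each event only to the regimen in use when it occurs. Label the result descriptive, because switching may be informative and progression is still judged against the earlier baseline.

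The cost is minor SAP wording and a small programming change. No new data are needed, since SAP 7.5 already calls for treatment duration by regimen. Any separately reported times for reduced regimens will be shorter, and with baseline-period rows alone those regimens have no result of their own.
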